9.8 Reporting Adverse Events

The Investigator is required to report all adverse events experienced by the patient from the day of the surgical procedure (Visit 2) until the patient completes Visit 3 (30 days after the surgical procedure) or withdraws early (prior to Visit 3). All adverse events (both serious and non-serious), regardless of their relatedness to the study device or procedure, must be reported in the Adverse Event eCRF. The investigator will evaluate the severity of the event, and its relatedness to the study device or procedure. Both severity and relatedness of all adverse events need to be entered in the Adverse Event eCRF.

Any necessary medical management of the event will be recorded in the patient's medical record/source document. All adverse events must be followed until resolution or until they become stable but ongoing.

The Investigator will record all adverse events (both serious and non-serious) in the source documents. Standard medical terminology should be used when recording adverse events. In addition, the following information should be recorded:

- Onset date
- Resolution date or date of death
- Severity of the event
- Action taken
- Event status (ongoing at study end or resolved)
- Relationship of adverse event to the device used in the study
- Relationship of the adverse event to the study surgical procedure
- Indication of whether the event is serious.

Data related to SAEs will be collected until event resolution, or until the event is considered stable, or until all attempts to determine the resolution of the event are exhausted. All adverse events that are unresolved at study completion (or early termination) will be recorded as ongoing at study end.

9.8.1 Procedures for Reporting Serious Adverse Events to the Sponsor

All SAEs that occur during the course of the study regardless of causality must be reported by the Investigator **within 24 hours** from the point in time when the Investigator becomes aware of the SAE. The SAE form should be submitted to the study medical monitor.

All serious adverse events, regardless of causality, should be collected and reported beginning with signing of the ICF through the follow-up visit.

Any SAEs that occur after the End of Study Follow-up Visit has concluded, including after the study has concluded, and that are **considered related to the study device or procedure by the Investigator** are considered reportable, and must be reported to the Sponsor **within 24 hours**.

The information collected by the site will include a minimum of the following: subject number; a thorough description (narrative) of the event, including its onset, relevant signs/symptoms, progression, treatment and outcome; and an assessment by the Investigator as to the severity of the event and relatedness to any/all study device(s) or study procedure(s).

The information reported on the SAEs report form should match the data provided by the site on the eCRF. The Investigator is also responsible for spontaneously reporting any subsequent follow-up information, including clinically relevant additional information, such as change in outcome.

In the event of death, the Investigator must report all available information to the Sponsor.

9.8.2 Procedures for Reporting Unanticipated Adverse Device Effects

Reporting UADEs to the Sponsor

The study site must report all SAEs, whether they are related to the device or procedure, to the Sponsor as soon as possible, but no later than 24 hours of becoming aware of the SAE.

Information not available at the time of the initial report (e.g., an end date for the UADE) must be updated within the safety database. In the event of a fatal or life-threatening event, any required follow-up information must be submitted to the Sponsor immediately, but no later than 10 calendar days of the initial report.

If the Sponsor determines an UADE presents an unreasonable risk to subjects, the Sponsor shall terminate all or a portion of investigations as soon as possible so as not to jeopardize the health of any patient.

Termination shall occur no later than 5 working days after the Sponsor makes this determination and no later than 15 working days after the Sponsor first receives notice of effect. Resumption of terminated studies can occur only with IRB and FDA approval.

Reporting UADEs to the FDA

For any observed or volunteered adverse event that is determined to be a UADE, the sponsor-investigator will submit an expedited safety report to the FDA's Center for Devices and Radiological Health. The expedited safety report will consist of:

- a completed Form FDA 3500A
- a cover letter analyzing the significance of the event

A copy of this safety report will be provided to all participating study investigators.

The completed [Form FDA 3500A](#) and cover letter will be submitted to the FDA as soon as possible and, in no event, later than 10 working days after the sponsor-investigator first receives notice of the adverse effect.

If, following receipt and investigation of follow-up information regarding an adverse effect that was previously determined not to be a UADE, the sponsor-investigator determines that the event does meet the requirements for expedited reporting, the sponsor-investigator will submit a completed [Form FDA 3500A](#) and cover letter as soon as possible, but in no event later than 10 working days, after the determination is made.

Subsequent to the initial submission of a completed [FDA Form 3500A](#), the sponsor-investigator will submit additional information concerning the reported adverse effect as requested by the FDA.

Reporting Adverse Effects to the IRB

For any adverse event determined to be a UADE, the sponsor-investigator will submit the completed [Form FDA 3500A](#) and cover letter to the IRB as soon as possible and, in no event, later than 10 working days after the sponsor-investigator first receives notice of the adverse effect.

Follow-up information to reported adverse effects will be submitted to the IRB as soon as the relevant information is available.

9.8.3 Reporting of Pregnancy

Details of all pregnancies in female participants and female partners of male participants will be collected after the start of study intervention and until last study visit.

If a pregnancy is reported, the investigator should inform the sponsor within 24 hours of learning of the pregnancy.

Abnormal pregnancy outcomes (e.g., spontaneous abortion, fetal death, stillbirth, congenital anomalies, ectopic pregnancy) are considered SAEs.

10 QUALITY CONTROL AND QUALITY ASSURANCE

10.1 Monitoring

Study progress will be monitored by United Health Products or its representative as frequently as necessary to ensure adequate and accurate data collection, protocol compliance and to determine that the study is being conducted in conformance with accepted regulatory requirements. Arrangements for monitoring visits will be made in advance, except in case of emergency. Details will be provided in the study specific Monitoring Plan.

10.2 Study Audit

The study may be audited to assess adherence to the Study Protocol. The consistency of the data presented in the report will be verified by either the Sponsor or designee. During the conduct of the study, process-related and facility-related audits may be performed as well. The clinical research site will be monitored by the study monitor to ensure correct performance of the study procedures and ensure that the study is conducted according to the relevant regulatory requirements. Electronic CRF entries will be verified with the source documentation, if applicable. In some cases, there are no source pages; therefore, verification is not necessary.

Regulatory authorities, the IRB, the Sponsor's quality assurance group, or all parties may request access to all source documents, eCRFs, and other study documentation for on-site audit or inspection. Direct access to these documents must be guaranteed by the Investigator,

who must provide support at all times for these activities. Quality control principles will be applied throughout the performance of this study.

11 STATISTICAL AND ANALYTICAL PLANS

A detailed Statistical Analysis Plan (SAP) will be written and approved prior to database lock. The SAP will describe all planned analyses based on the statistical design of this study and the subsequent data collected. A brief overview of key statistical analyses is provided below.

11.1 Determination of Sample Size

A non-inferiority comparison will be performed to determine if the hazard ratio with an overall sample size of 212 subjects (106 HemoStyp group and 106 Surgicel group) achieves 80% power at a 0.05 significance level when the hazard ratio is actually 1.33 (median survival is 3.0 minutes for HemoStyp and 4.0 minutes for Surgicel). The non-inferiority ratio is 0.75 (corresponding to margin of 1 minute). It is anticipated that the proportion of subjects observed with the event during the study is 0.90 for the HemoStyp group and 0.92 for the Surgicel group. These results assume that the hazard ratio is constant throughout the study and that Cox proportional hazards regression or the non-inferiority log-rank test is used to analyze the data.

It is anticipated that approximately 710 subjects will be screened to randomize approximately 236 subjects with an anticipated drop-out rate of approximately 10%.

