11.2.2 Analysis Populations

Intent-To-Treat Population (ITT): The ITT population will include all subjects who are randomized to HemoStyp or Surgicel. The efficacy analysis will be performed using the ITT population.

The Per Protocol population (PP): The PP population will include all subjects who are not major protocol violators with regards to inclusion/exclusion criteria, randomization, and have availability of scheduled data for all treatments and efficacy evaluations.

Safety Population: The safety population will include all subjects who are treated with any amount of HemoStyp or Surgicel. Safety analyses will be performed using the safety population and subjects will be analyzed according to the treatment they actually receive.

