11.2.5 Efficacy Analyses

Primary Endpoint

The time to hemostasis will be measured from start of study treatment to the achievement of hemostasis at the target bleeding site (TBS), or to the end of the 10-minute observation period. The time to hemostasis will be considered as censored at the end of the 10-minute observation period. Time to hemostasis will be quantified in minutes according to its nominal time point. When re-bleeding occurs, and the cessation of bleeding is again achieved at a later time point, the effective time to hemostasis will be the latter time point. The time to hemostasis will be the time from start of study treatment to that last effective hemostatic time point.

Secondary Endpoints

- Percentage of subjects achieving hemostasis at the target bleeding site at 2 minutes and at 5 minutes following the start of study treatment;
- Percentage of subjects with intraoperative hemostasis at the target bleeding site;
- Percentage of subjects with intraoperative re-bleeding from the target bleeding site post hemostasis;
- Postoperative re-bleeding from the target bleeding site requiring surgical re-exploration up to 30 days after surgery.

Analysis of the Primary Endpoint

The primary endpoint analyses will be based on ITT population. The primary analysis is the test of non-inferiority of HemoStyp compared with Surgicel. Cox proportional hazards regression or log-rank test will be used for the analysis of non-inferiority.

The null hypothesis for the testing of the primary endpoint is described below:

H0: HemoStyp is inferior or worse than Surgicel by more than 1 minute for median survival (HR<0.8);

H1: HemoStyp is inferior to Surgicel by less than 1 minute for median survival (HemoStyp is not inferior to Surgicel) ($HR > 0.8$);

If the lower bound 95% confidence interval of $HR > 0.8$, we conclude that HemoStyp is not inferior to Surgicel.

The primary endpoint analyses will also be performed on the PP population.

Analyses of Secondary Endpoints

A two-sided z-test with pooled variance will be used to test the difference for each secondary endpoint. The 95% confidence intervals (CIs) for each secondary endpoint in each group (HemoStyp or Surgicel) will be provided.

Secondary endpoints will be assessed at significant level of 0.05 in the order listed below after achievement of a significant result for the primary endpoint:

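### Section 11.1's printed inputs give about 98% power at 212 subjects, not 80%, and its event proportions contradict its assumed hazard ratio of 1.33

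*Combined protocol and SAP*

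**What the plan says.** Section 11.1 (Determination of Sample Size) and the sample-size paragraph of the synopsis give the same calculation. They claim that "an overall sample size of 212 subjects (106 HemoStyp group and 106 Surgicel group) achieves 80% power at a 0.05 significance level". The remaining inputs are:

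- Assumed effect: "when the hazard ratio is actually 1.33 (median survival is 3.0 minutes for HemoStyp and 4.0 minutes for Surgicel").
- Margin: "The non-inferiority ratio is 0.75 (corresponding to margin of 1 minute").
- Events: "the proportion of subjects observed with the event during the study is 0.90 for the HemoStyp group and 0.92 for the Surgicel group".
- Model: "These results assume that the hazard ratio is constant throughout the study", with Cox regression or a non-inferiority log-rank test.

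Section 11.1 does not say whether the 0.05 is one-sided or two-sided.

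Two statements in Section 11.2.5 bear on the calculation. On follow-up: "The time to hemostasis will be considered as censored at the end of the 10-minute observation period". On the decision rule: "If the lower bound 95% confidence interval of $HR > 0.8$, we conclude that HemoStyp is not inferior to Surgicel". The margin there is 0.80, not 0.75.

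**The concern.** A true hazard ratio of 1.33 in favour of HemoStyp, tested against a margin of 0.75, is a long distance to detect: the ratio of the two is 1.77. With more than 190 events, power should be far above 80%. The event proportions also run the wrong way, since the arm assumed to reach hemostasis faster is given the smaller share of events within the same 10 minutes.

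This paragraph is the only justification for the size of a pivotal study meant to support a marketing application. If 1.33 and 0.75 were the real assumptions, the power is understated. If 212 came from other inputs, the printed hazard ratio or margin is wrong. A reader cannot tell which.

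**Working it through.** **Inputs (Section 11.1 unless noted).** 106 per arm; true HR 1.33; margin 0.75, or 0.80 from Section 11.2.5; event proportions 0.90 and 0.92. The two-sided 95% interval corresponds to one-sided α = 0.025. One-sided 0.05 is shown as well because sidedness is not stated.

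**Formulas (Schoenfeld, 1:1 allocation).**

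- Power = Φ(√(D/4) × ln(HR/margin) − z₁₋α)
- Events needed = 4(z₁₋α + z_power)² / [ln(HR/margin)]²

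**Step 1: try to reproduce the 80%.** D = 106 × (0.90 + 0.92) = 192.9 and √(D/4) = 6.945. At margin 0.75, ln(1.33/0.75) = 0.5729 and the product is 3.978, so power = Φ(3.978 − 1.960) = 97.8%. At margin 0.80, ln(1.33/0.80) = 0.5083 and the product is 3.530, so power = Φ(3.530 − 1.960) = 94.2%.

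| Reading, D = 192.9 | one-sided α 0.025 | one-sided α 0.05 |
|---|---|---|
| HR 1.33, margin 0.75 (Section 11.1) | 97.8% | 99.0% |
| HR 1.33, margin 0.80 (Section 11.2.5) | 94.2% | 97.0% |
| Superiority at HR 1.33 | 50.8% | 63.1% |
| True HR 1.0, margin 0.75 | 51.5% | 63.8% |
| True HR 1.0, margin 0.80 | 34.1% | 46.2% |

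None is close to 80%.

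**Step 2: is it the choice of formula?** At margin 0.75 and α = 0.025, Freedman's formula gives 97.2%, a Wald variance based on events per arm gives 97.8%, and an exponential rate-difference test gives 92.9%. Cox simulations with exponential medians of 3 and 4 minutes, a 30-second inspection grid and censoring at 10 minutes gave about 97% to 98% at margin 0.75 and 93% to 94% at margin 0.80.

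**Step 3: what would give 80%?** At 192.9 events, 80% needs HR/margin = 1.497 (α = 0.025) or 1.431 (α = 0.05), against the stated 1.33/0.75 = 1.773. With α = 0.025 the true HR would have to be 1.12 at margin 0.75, or 1.20 at margin 0.80. Conversely, with HR 1.33 and α = 0.025, 80% needs far fewer subjects:

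| Margin | Events for 80% | Total N at 91% events | Total N at 86.2% events |
|---|---|---|---|
| 0.75 | 95.7, so 96 | 105.1, so 106 | 111.0, so 112 |
| 0.80 | 121.5, so 122 | 133.5, so 134 | 141.0, so 142 |

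Totals are rounded up to equal arms. The 86.2% is the average proportion under exponential times (Step 4).

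**Step 4: event proportions against the assumed HR.** With proportional hazards and the same 10-minute cut-off in both arms, S_HemoStyp(10) = S_Surgicel(10)^HR.

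- The stated pair implies HR = ln(0.10)/ln(0.08) = 0.91, which favours Surgicel.
- If Surgicel is 0.92 and HR is 1.33, HemoStyp must be 1 − 0.08^1.33 = 0.965.
- If HemoStyp is 0.90 and HR is 1.33, Surgicel must be 1 − 0.10^(1/1.33) = 0.823.
- Exponential times with medians 3 and 4 minutes give 1 − 2^(−10/3) = 0.901 and 1 − 2^(−10/4) = 0.823, mean 0.862.

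**Step 5: does a consistent pair change the power?** With α = 0.025:

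| HemoStyp / Surgicel | Events at N = 212 | Margin 0.75 | Margin 0.80 |
|---|---|---|---|
| 0.90 / 0.92 (as printed) | 192.9 | 97.8% | 94.2% |
| 0.901 / 0.823 | 182.7 | 97.2% | 93.0% |
| 0.965 / 0.92 | 199.8 | 98.2% | 94.9% |

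The inconsistency is real but worth under one point at margin 0.75 and about one point at 0.80.

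**The case against.** The arithmetic itself was not disputed. The strongest objections concern emphasis and remedy.

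- **98% is not the power of the planned test.** The decision rule uses 0.80. That value also fits a one-minute margin on a 4-minute Surgicel median (4/5), whereas 0.75 is 3/4. This is fair: under the decision rule as written the figure is 94.2%. It still does not recover 80%. The conflict between margins is a separate point.
- **The consequence is small.** The error is towards excess power, and correcting it changes no estimand, test or decision rule. This stands, and is why the point is a correction to the text and not a threat to the trial. The event-proportion error alone may be a one-digit slip (0.92 for 0.82), although the documents do not say so.
- **Printing 97% may falsely reassure.** The high power rests wholly on HemoStyp being a third faster, and the Introduction supports its speed only with animal and laboratory work. If the arms are truly equal, power at 193 events is about 52% (margin 0.75) or 34% (margin 0.80). This is a good reason to print a sensitivity figure at HR 1.0 beside the corrected power. It is not a reason to leave 80% in place.

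The total needed for 80% at margin 0.75, 106, equals the printed number per arm, which might suggest that a total was entered as a per-arm size. But margin 0.80 at one-sided 0.05 also leads to 106 (95.7/0.91 = 105.2), so the coincidence identifies no cause.

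**Conclusion.** The concern holds on both counts. The stated 80% does not follow from the stated inputs. The power is 97.8% at margin 0.75, or 94.2% at margin 0.80, reading the rule as a two-sided 95% interval; one-sided 0.05 raises these to 99.0% and 97.0%. The event proportions contradict a constant hazard ratio of 1.33 under equal 10-minute censoring.

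The power figures assume proportional hazards, 1:1 allocation, 212 analysed subjects and no adjustment for the interim analysis named in the synopsis. The second count also assumes no early loss that differs by arm; the documents describe none. The trial is not too small under its own assumptions. What fails is the reproducibility of the reason for 212. It should be fixed, with high confidence.

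**What to change.** In Section 11.1 and the synopsis, leaving the sample size unchanged:

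1. State the sidedness of the 0.05.
2. Replace 0.90/0.92 with a pair that fits the assumed hazard ratio and medians. If times are taken as exponential, which the protocol does not state, this is 0.90/0.82.
3. Restate the power with the single margin the sponsor confirms when reconciling Sections 11.1 and 11.2.5.
4. If 212 was derived from other inputs, print those as the reason for it.
5. Say which analysis set the 212 refers to. Section 11.2.2 says "The ITT population will include all subjects who are randomized to HemoStyp or Surgicel", while Section 11.2.7 restricts all analyses to treated subjects. If all 234 to 236 randomized are analysed, power under exponential times is about 98% (margin 0.75) or 95% (margin 0.80).

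Possible wording:

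> Assuming exponential times with medians of 3 minutes (HemoStyp) and 4 minutes (Surgicel) and censoring at 10 minutes, 212 analysed subjects give about 183 events. With a two-sided 95% confidence interval, power at a hazard ratio of 1.33 is about [97% for margin 0.75 / 93% for margin 0.80], before any interim-analysis adjustment.

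A sentence giving power at a hazard ratio of 1.0 would be a useful addition.

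The cost is a text change in two places. One power figure cannot be printed until the margin is settled. If 0.80 is confirmed, only Section 11.1 and the synopsis change. If 0.75 is confirmed, the hypotheses and decision rule in Section 11.2.5 change too, which is a change to the analysis.

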11.2 Analysis to be Conducted

11.2.1 General Conventions

Summary tables (descriptive statistics and/or frequency tables) will be provided for all demographic, baseline variables, efficacy and safety variables by treatment group. Continuous data will be summarized in terms of mean, standard deviation (SD), median, quartiles (Q1 and Q3), minimum, maximum and number of valid observations. Categorical data will be summarized in terms of the number of subjects, frequency counts and percentages. All data will also be presented in by-patient listings.

11.2.2 Analysis Populations

Intent-To-Treat Population (ITT): The ITT population will include all subjects who are randomized to HemoStyp or Surgicel. The efficacy analysis will be performed using the ITT population.

The Per Protocol population (PP): The PP population will include all subjects who are not major protocol violators with regards to inclusion/exclusion criteria, randomization, and have availability of scheduled data for all treatments and efficacy evaluations.

Safety Population: The safety population will include all subjects who are treated with any amount of HemoStyp or Surgicel. Safety analyses will be performed using the safety population and subjects will be analyzed according to the treatment they actually receive.

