5.2 Secondary Endpoints

Secondary efficacy endpoints include:

- Percentage of subjects achieving hemostasis at the target bleeding site at 2 minutes, 5 minutes and 10 minutes following the start of study treatment;
- Percentage of subjects with intraoperative hemostasis at the target bleeding site;
- Percentage of subjects with intraoperative re-bleeding from the target bleeding site post hemostasis; and
- Postoperative re-bleeding from the target bleeding site requiring surgical re-exploration up to 30 days after surgery.

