6.4 Removal of Subjects from Study

In accordance with the current revision of the Declaration of Helsinki and the Code of Federal Regulations, a subject has the right to withdraw from the study at any time for any reason without prejudice to his/her future medical care by the physician or the institution. Should a subject (or subject's legally authorized guardian/representative) decide to withdraw; all efforts will be made to collect any adverse events they have experienced, if applicable. Subjects who withdraw or are terminated early from the study may be replaced. Participation may be terminated prior to completing the study for any of the reasons listed below (reasons that do not fit the categories below will be documented as "other").

Withdrawal of Consent:

If a subject chooses to withdraw early from the study, the eCRF completion page should be completed. When a subject's participation is terminated prior to completing the study, the reason for withdrawal is to be documented on the eCRF and in the source documentation.

Surgical:

The Investigator must withdraw a subject intraoperatively for the following reasons:

- Subjects do not have an appropriate target bleeding site.
- Subject develops coagulation diathesis post-operatively such as DIC (Disseminated Intravascular Coagulation).

Death:

When possible, the cause of death will be documented.

Lost to Follow-up:

All subjects should be encouraged to return for protocol required clinic visits for evaluation during the study follow-up period. If a patient is unable to return for a clinic visit or unable to be contacted by telephone, attempts to contact the patient should be documented in the source documents. Only after failing to contact the patient at the final follow-up visit, the patient will be considered lost to follow-up and the primary reason for early termination will be completed in the eCRF.

Site Termination or Study Termination:

The Sponsor may terminate a site or study at any time. When this occurs all subjects at the site will be withdrawn and documented as early termination. Reasons for site or study termination may include, but are not limited, to the following:

- Administrative concerns (e.g., inadequate patient enrollment, investigator/institution non-compliance, change of business strategy, etc.).

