7.3 Day 30 ± 7 (Visit 3)

From Day 0 through Day 30, subjects will be carefully monitored for any re-bleeding or need for exploratory surgery at the surgical site due to re-bleeding episodes. Any events of re-bleeding and/or requirement for additional surgery to address bleeding will be recorded and completely described.

On Day 30, subjects will report to the clinical for the follow-up procedures:

- Review and record concomitant medication;
- Assess for any re-bleeding at the target site; and
- Assess and record any adverse events or any adverse device reactions.

Following this, participation in the study will be completed.

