11.2.7 Handling of Missing Data

All analyses will be performed only on subjects undergoing surgical procedures during which treatment (HemoStyp or Surgical) is applied to target bleeding sites. There will be no imputation of missing data for any parameters or for early terminated subjects.

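### Read literally, the Per Protocol definition lets a missing 30-day outcome remove a complete 10-minute primary endpoint from the additional PP non-inferiority analysis

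*Combined protocol and SAP*

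**What the plan says.** - **PP set.** Section 11.2.2 excludes major violators of the eligibility criteria or randomization, and also requires that members "have availability of scheduled data for all treatments and efficacy evaluations". It gives one PP definition for all endpoints.
- **Use of PP.** Section 11.2.5 makes ITT primary and adds: "The primary endpoint analyses will also be performed on the PP population". I find no planned PP analysis of any secondary endpoint.
- **Primary endpoint.** Section 11.2.5 closes it within the operation: "The time to hemostasis will be considered as censored at the end of the 10-minute observation period".
- **30-day endpoint.** Section 5.2 counts this among the secondary efficacy endpoints: "Postoperative re-bleeding from the target bleeding site requiring surgical re-exploration up to 30 days after surgery". The Visit 3 list in section 7.3 (Day 30 ± 7) contains the item "Assess for any re-bleeding at the target site; and", and Table 1.1 schedules it.
- **Missing data.** Section 11.2.7: "There will be no imputation of missing data for any parameters or for early terminated subjects".
- **Losses.** Section 11.1 plans to randomize about 236 subjects "with an anticipated drop-out rate of approximately 10" percent and does not say when drop-out occurs. Section 6.4 lists death, consent withdrawal, post-operative coagulation diathesis, site closure and loss to follow-up as ways out. On the last it says: "Only after failing to contact the patient at the final follow-up visit, the patient will be considered lost to follow-up".

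**The concern.** A PP analysis should remove subjects whose conduct departed from the protocol in a way that blurs the treatment comparison. Absence of a 30-day outcome says nothing about whether the hemostat was applied correctly or the stopwatch assessment was valid. The rule would discard sound primary data for an unrelated reason.

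The exits that leave the 30-day outcome unrecorded all come after randomization, and most come after the primary endpoint. Some, such as death or post-operative coagulopathy, may be connected with bleeding. Selecting on them can unbalance the arms. If the PP and ITT results then differed, a reader could not tell whether protocol adherence or the population rule was responsible.

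**Working it through.** **Textual check**

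1. Membership requires scheduled data for every efficacy evaluation (11.2.2).
2. Re-bleeding to 30 days is an efficacy endpoint (Synopsis, 5.2) with a scheduled assessment at Visit 3 (7.3, Table 1.1).
3. A 30-day outcome that is missing stays missing (11.2.7).
4. The primary non-inferiority analysis is repeated on this same set (11.2.5).
5. Randomization takes place during surgery, once a qualifying bleeding site is found (7.2). The primary data are complete 10 minutes after application or, counting the 5-minute check after presumed hemostasis, within 10 + 5 = 15 minutes.

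A subject can therefore satisfy everything the primary analysis needs and still fail the PP rule. No section makes an exception.

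**Inputs for the size**

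From 11.1: 236 randomized (234 elsewhere in the protocol), 212 evaluable, 10% drop-out, hazard ratio 1.33, event proportions 0.90 and 0.92 (mean 0.91), margin 0.75. From 11.2.5: margin 0.8, judged by the lower bound of a 95% interval, so I use two-sided 0.05. Assumptions of mine: the timing of drop-out, and no other PP exclusions.

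**The plan's own figures**

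- 212/(1 − 0.10) = 235.6, so 236 reproduces. 212 × 1.10 = 233.2, rounded up, gives the other figure, 234.
- The 212 for 80% power does not reproduce. Events needed = 4(1.96 + 0.842)²/[ln(1.33/0.75)]² = 96, and 96/0.91 gives 106 subjects in total. With 212 subjects the same inputs give 97.8% power. That is a separate matter, and this point does not rest on it.

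**Subjects lost**

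236 × 0.05 = 11.8, about 12. 236 × 0.10 = 23.6, about 24. Starting from 234, 10% is about 23.

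**Precision**

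SE of the log hazard ratio = 2/√events. With 236 × 0.91 = 214.8 events it is 0.1365; with 212 × 0.91 = 192.9 events it is 0.1440. The ratio is √(236/212) = 1.055, so the interval is about 5% wider on the log scale.

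**Power**

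Power = Φ( ln(1.33/margin) × √(events/4) − 1.96 )

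| Late loss | PP subjects | Events | Margin 0.80 | Margin 0.75 |
|---|---|---|---|---|
| 0% | 236 | 214.8 | 96.1% | 98.7% |
| 5% | 224 | 203.8 | 95.2% | 98.3% |
| 10% | 212 | 192.9 | 94.2% | 97.8% |

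Worked example, 10% late loss against 0.80: 0.5083 × √48.23 − 1.96 = 1.57, and Φ(1.57) = 0.942.

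**The case against.** Several objections have force.

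- **ITT decides.** Section 11.2.5 says only that the analysis is also run on PP. It does not call PP co-primary or supporting, and it has no rule for discordant results. A reader might infer that the non-inferiority claim is at risk; the documents do not support that.
- **Day 30 is inferred.** Section 11.2.2 does not name it. The reading comes from combining that section with the endpoint list and visit schedule.
- **A missed visit is not always a missing outcome.** Section 7.3 monitors re-bleeding from Day 0 through Day 30, and section 6.4 allows telephone contact. A re-exploration in the first week is on record whether or not the subject attends Visit 3. It would be too strong to say that everyone who misses Visit 3 is dropped.
- **The loss was budgeted.** A PP set of 212 equals the planned evaluable number, and section 6.4 allows withdrawn subjects to be replaced. This answers much of the concern about size but not the concern about selection.
- **Larger power losses need other inputs.** A true hazard ratio nearer 1 would show a bigger drop, but the plan assumes 1.33, where the drop is 1 to 2 points.
- **Detail is deferred.** Section 11 describes itself as an overview and promises a full SAP before database lock. A PP set that requires study completion is also a recognisable convention. Even so, the present rule is stated, and unless changed it would carry over.

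**Conclusion.** The point stands as a minor one. As worded, the PP rule can exclude subjects with a complete primary endpoint because their 30-day outcome is unavailable: lost, withdrawn, or died before it was recorded. The main harm is selection on post-endpoint events. Its direction cannot be determined from the documents, and a reader should not infer that it favours either product.

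The loss of precision is secondary. The 24 of 236 is an upper figure, not an estimate: it assumes that the whole planned drop-out falls after the endpoint and that each such subject lacks the 30-day outcome. The power figures also rest on the plan's hazard ratio and event proportions and on two-sided 0.05.

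**What to change.** Replace the data-availability clause in section 11.2.2, or set the following in the SAP. For the primary endpoint, the PP set comprises subjects with no major violation of eligibility, randomization or treatment and with a valid intraoperative time to hemostasis, whether an event or censored at 10 minutes. Require 30-day data only for a PP analysis of 30-day re-bleeding, if one is made.

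The cost is one sentence and no new data. Because the trial is open-label and has an interim analysis after 118 subjects reach the 30-day visit, the change is best made before that look, so that it cannot appear to be driven by results.
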